#### **10.2. Other risks that might result from study procedures**

There is the unknown risk of radiation exposure as part of the PET scanning procedure. However, the radiation dose provided has not been found to be associated with any harm. Subjects exceeding the yearly radiation dose limit (20 mSv) will be excluded from study. There is the risk of bruising and discomfort from venipuncture. Some subjects might find some questions on the screening tests (e.g., SCID) uncomfortable.

## 11. PREMATURE WITHDRAWAL/DISCONTINUATION CRITERIA

Subjects are advised in the consent form that they are free to withdraw from the study at any time without prejudice, and may be withdrawn at the Investigators discretion.

Trial will also be terminated should subject develop or be found to have any condition that might compromise subject safety (e.g., unstable vitals, presence of abused drug in urine) or confound interpretation of primary PET outcome measure.

If the subject withdraws from the study at any time prior to Xyrem® ingestion, they will be paid a pro-rated amount, and are free to leave at any time. If they withdraw from the study after Xyrem® ingestion, the subject must remain in the PET Centre, monitored by the anesthesiologist, until such time that the anesthesiologist determines it is safe for the subject to leave. Subject will then be paid a pro-rated amount, and allowed to leave by taxi or with companion. All data collected up to the point that the subject withdraws will be used (if applicable).

## 12. SAFETY VARIABLES AND ANALYSIS

Prior to and following Xyrem® administration the anesthesiologist will monitor the subject's level of consciousness and vital signs. The physiological monitor in the PET Centre unit will allow continuous display of oxygen saturation, HR, respiratory rate and intermittent blood pressures (every 15 minutes or more frequent if indicated).

### 12.1. Adverse Events

**Adverse events** will be assessed at each study visit following administration of the first PET radiotracer (Baseline scan day). Study staff will question the subject directly asking: how they are feeling following the scans/Xyrem®; how have they been feeling since last visit. All AEs, whether reported by the subject or observed by study staff/investigators, will be recorded (as a diagnosis not per symptom: i.e. common cold vs. sore throat, sinus congestion, etc.) on the AE log along with a brief description, start date/resolution date and any action taken (medications, Dr. visit, etc.). The AE log will be initiated by the QI, who will make the determination on relationship of the AE to the investigational drug. All AEs determined by the QI to have a causal relationship with the investigational product or as a result of study procedures, will be reported to CAMH REB as part of the annual ethics approval renewal process. Examples of this would include, but not be limited to: claustrophobia from either PET or MRI scanner; nausea and/or vomiting, headache – known possible reactions to Xyrem® as per Xyrem® monograph (depending on severity as assessed by QI).

Final contact with the subjects occurs the day after Xyrem® administration, via phone call from RC and/or PI. During this call, RC and/or PI will enquire about any new AEs or unresolved AEs that have been recorded in the subjects file. If the AE is still unresolved, they will be marked as ongoing, and the QI will determine whether the AE requires any further follow-up. This will be documented on the log, with follow-up calls/visits to occur if/as necessary using the unscheduled visit forms.

### 12.2. Serious Adverse Events

As defined by Health Canada, a **serious adverse event (SAE)** is an adverse event that:

- requires in-patient hospitalization or prolongation of existing hospitalization
- causes congenital malformation
- results in persistent or significant disability or incapacity
- is life threatening
- results in death

Important medical events that may not result in death, be life-threatening or require hospitalization, may be considered an SAE when, based upon medical judgment, may jeopardize the subject and may require medical or surgical intervention to prevent one of the outcomes listed above.

**A Serious Unexpected Adverse Drug Reaction (SUDAR)** as defined by Health Canada is a serious adverse drug reaction that is not identified in nature, severity or frequency in the risk information set out in the investigator's brochure or on the label of the drug.

If any AEs recorded are determined by the QI to be SAEs or SUADRs, they must be reported, within a specified time frame to:

- 1) CAMH REB: QI must complete and sign the CAMH REB Serious Adverse Events form and submit to the REB within 48 hours of knowledge. The QI will include a description of the event in sufficient detail to allow for a complete medical assessment of the case and independent determination of possible causality.
- 2) Health Canada: As required under Food and Drug Regulations, Part C, Division 5: During the course of a clinical trial, the sponsor/investigator shall inform the Minister of any serious unexpected adverse drug reaction in respect of the drug that has occurred inside or outside Canada as follows:
  - (a) if it is neither fatal nor life threatening, within 15 days after becoming aware of the information; and
  - (b) if it is fatal or life threatening, within seven days after becoming aware of the information.

The sponsor/investigator shall, within eight days after having informed the Minister, submit a complete report in respect of that information that includes an assessment of the importance and implication of any findings made.

- 3) Jazz Pharmaceuticals: The investigators will inform Jazz Pharmaceuticals of any SAEs occurring within the study subject population. Jazz will be copied (via [[contact]](mailto:[contact])) on the CAMH REB SAE report, any subsequent correspondence, and will be provided a copy of the CIOMS form I report.

For expedited reporting to Health Canada and Jazz Pharmaceuticals, the investigators will use the CIOMS form I.

### **13. STATISTICAL ANALYSIS**

The Biostatistical Consulting Service at CAMH, who provided the power calculations, will continue to advise on all statistical analyses to be conducted. Prior to analysis, data will be screened to ensure that underlying assumptions for statistical procedures are met. Should any demographic characteristic be found to be associated with outcome measures, they will be included as covariates in subsequent analyses. Changes in raclopride binding in whole striatum will be tested using a mixed model, with raclopride binding the dependent variable and time (baseline vs. one hour post-Xyrem® and vs. 7 hours post- Xyrem®) as the categorical independent variable. An unstructured covariance structure will be assumed. Should a significant time effect be detected, a series of Bonferroni-adjusted pairwise comparisons will be carried out. Changes in DTBZ will be assessed using a paired t-test. Subcompartments of striatum will be examined in a separate exploratory analysis. An exploratory correlation (Pearson) will investigate relationship between DTBZ binding changes at five hours (dopamine buildup) vs. raclopride changes at 7 hours (release of dopamine that had been "built-up").

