Xyrem®, taken at night, is thought to act by providing continuous "refreshing" sleep to patients with narcolepsy resulting in less periods of daytime sleepiness. The mechanisms of this action are unknown; however, the manufacturer suggests that, based on animal literature, a key action might be a reduction in brain dopaminergic activity during sedation ([3] ; see also below). In this regard, some animal data suggest that an acute dose of Xyrem® depresses activity of brain dopamine neurones and, as a result, dopamine is not released from the nerve ending (see below). On the other hand, investigators leading a study of Xyrem® in Parkinson's disease patients who have sleep problems suggest a different mechanism: that Xyrem®-induced improvement of daytime sleepiness might be caused by above-normal release of dopamine (acting as a modest dopamine-delivering stimulant) during drug withdrawal (which would occur at daytime), as the dopamine built up in the neurone during sleep/sedation is released during the day [4].

Animal data (since 1966 [5]), which could address the above questions are still contradictory and sparse on the nature of GHB-dopamine interactions [6-10] (e.g., review "Does GHB inhibit or stimulate central DA release?") [11]. Cruz and colleagues, on the basis of some electrophysiological findings speculate that "recreational" doses of GHB could *stimulate* dopamine neurones, but that at "higher" concentrations dopamine release might be inhibited [12]. Missing from experimental animal studies are data convincingly showing effects of GHB "withdrawal" on dopamine (i.e., is withdrawal associated with a potentially beneficial dopaminergic hyperactivity?).

Animal findings, however, can only suggest what might occur in the human and need to be confirmed in the clinically relevant human.

In light of the speculations above, the available animal findings, and our preliminary brain imaging findings in normal subjects described below, we wish to determine in a brain imaging study whether Xyrem® might produce a concentration and time-dependent biphasic change in dopamine activity in

(Xyrem®-naïve) patients with narcolepsy. We will also include a group of control subjects in order to determine whether this proposed mechanism of action of Xyrem® might or might not be dependent on disease state.

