Taken together, the preliminary raclopride and DTBZ findings, provide the first hint that Xyrem® might induce, in the normal human brain, initial buildup of intraneuronal dopamine and decreased release, followed hours later by above-normal dopamine release. We now aim to determine whether either of these changes occurs in brain of patients with narcolepsy, the indication for which Xyrem® is approved, following a single dose of the drug.

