### 3. OBJECTIVE AND HYPOTHESES

Our **Trial Objective** is to establish, in Xyrem®-naïve patients with narcolepsy and in matched controls, whether a single dose of Xyrem® causes changes in striatal binding of C-raclopride and C-DTBZ that would suggest decreased activity of brain dopamine neurones during the initial sedation and increased dopaminergic activity during Xyrem® withdrawal.

Our **WORKING MODEL**, based on our preliminary human PET brain data, is that an initial action of Xyrem® is to cause, during sedation (which is very fast onset with Xyrem®), depressed activity of nigrostriatal dopamine neurones and dopamine release together with marked intraneuronal biosynthesis of dopamine. At this early time, intraneuronal concentrations of dopamine (competing with C-DTBZ at VMAT2) will be high whereas extraneuronal levels of dopamine (competing with C-raclopride at the dopamine receptor) will be low because (we predict) Xyrem® causes accelerated synthesis of dopamine while depressing activity of dopamine neurones.

During drug withdrawal, dopamine that has been building up inside the neurone is released, leading to increased extraneuronal dopamine (accompanied by decreased raclopride binding at the dopamine receptor) and a normalization of dopamine levels inside the neurone. The modestly increased dopamine activity might persist somewhat in drug withdrawal and be beneficial to the patient.

Our **HYPOTHESES**, based on our pilot data and employing a five scan approach, are that, relative to baseline, striatal 1) **C-raclopride binding** will be increased one hour post-Xyrem® but decreased at seven hours, suggesting decreased and increased neuronal dopamine release, respectively, at these times; and 2) **C-DTBZ binding** will be decreased at five hours post-Xyrem®, suggestive of increased intraneuronal vesicular dopamine buildup during Xyrem® exposure. We predict that this biphasic change in dopamine will occur in both narcolepsy and in healthy control study groups.

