## 5. STUDY PARTICIPANTS

### 5.1. Sample Size

A maximum of 15 patients diagnosed with narcolepsy, who are not currently being treated with stimulant drugs (e.g. Alertec®, Ritalin®, or Dexedrine®) to manage their narcolepsy, and a maximum of 15 healthy controls, will complete all study procedures.

Monte Carlo simulations [17] (>10,000) were performed using BP estimates and standard deviations derived from our data in normal subjects and assumed mixed models analysis and constant standard deviations, with full maximum likelihood for evaluation and time treated as categorical variable to facilitate pre-planned comparisons of outcome values. Results indicate that a sample of 15 will provide sufficient power (>80%, 0.05 alpha) to detect changes (baseline vs. GHB day scans, within subject comparisons) of the magnitude observed in the small pilot study for both raclopride and DTBZ binding.

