## 7. EFFICACY VARIABLES AND ANALYSIS

The **primary endpoint** is the change in C-raclopride or C-DTBZ BP in whole striatum, caudate, putamen, and bilateral sub-compartments of the striatum, from baseline scan vs. that at one, 5 and 7 hour scans.

The **secondary endpoint** is the blood concentration of GHB (expressed as the area under the curve; AUC) at 0.5, 1, 3, 5 and 7 hours following ingestion of GHB.

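### Section 13 has no group or group-by-time term, so no planned analysis estimates the patient–control difference in change, and it does not say whether the tests are run by group

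*Combined protocol and SAP*

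**What the plan says.** **Purpose of the controls.** Section 2 (Background and Rationale) says the control group is there to "determine whether this proposed mechanism of action of Xyrem® might or might not be dependent on disease state". The pilot-data part of Section 2 ends with an aim for patients specifically, to "determine whether either of these changes occurs in brain of patients with narcolepsy".

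**Hypotheses.** Section 3 states: "We predict that this biphasic change in dopamine will occur in both narcolepsy and in healthy control study groups".

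**Sample size.** Section 5.1 allows up to 15 patients "and a maximum of 15 healthy controls, will complete all study procedures". It states that "a sample of 15 will provide sufficient power (>80%, 0.05 alpha) to detect changes (baseline vs. GHB day scans, within subject comparisons").

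**Endpoint.** Section 7 defines the primary endpoint as change in binding "from baseline scan vs. that at one, 5 and 7 hour scans", without reference to group.

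**Analysis.** Section 13 models raclopride in whole striatum with "time (baseline vs. one hour post-Xyrem® and vs. 7 hours post- Xyrem®) as the categorical independent variable" and an unstructured covariance. It continues: "Should a significant time effect be detected, a series of Bonferroni-adjusted pairwise comparisons will be carried out". DTBZ change gets a paired t-test. Sub-compartments and one Pearson correlation are exploratory. Demographic characteristics associated with outcome become covariates. Diagnosis does not appear.

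**The concern.** Whether a mechanism depends on disease state is a question about a difference in change between two groups. In a repeated-measures model that is the group-by-time term, and for DTBZ it is a comparison of two mean changes. Section 13 contains neither, so the plan carried out exactly as written gives no estimate for the question that justified adding controls.

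The analysis set is also open. A model with time as its only factor can be fitted to each group of up to 15 or to all 30 subjects. Under pooling, a response confined to controls could be reported as a drug effect and read as holding in patients, who are the subject of the aim at the end of Section 2. The data are open-label, so a choice left open could be made after results are seen.

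**Working it through.** **1. Does any text supply the group comparison?**

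| Place | What it covers | Between-group contrast? |
|---|---|---|
| Section 3 | Change predicted in both groups | No |
| Section 5.1 | Within-subject power, sample of 15 | No |
| Section 7 | Change from baseline | No |
| Section 13, raclopride | Time only | No |
| Section 13, DTBZ | Paired t-test | No |
| Section 13, covariates | Demographic characteristics | No |

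The covariate sentence does not fill the gap. Diagnosis is not a demographic characteristic, and a covariate main effect does not estimate a difference in change.

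**2. The plan's own power figure.** Section 5.1 prints no SD and no binding values, so its power above 80% cannot be reproduced. In SD units, a two-sided paired t-test at 0.05 with n = 15 (noncentral t, noncentrality d√15, 14 df) reaches 80% power at d = 0.778. This is the benchmark effect below. It is a single contrast without adjustment.

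**3. If the data were pooled and only controls responded.** Assumptions: 15 per group; equal SD of change in both groups; two-sided 0.05; in controls +0.778 SD at 1 h and −0.778 SD at 7 h; no change in patients. The rule is the 2-df time test at 0.05 (as Hotelling's test on the two change scores), then baseline contrasts at 0.05/2. There were 200,000 simulated trials for each correlation between the two changes.

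| Correlation | Time test significant | At least one contrast | Both, predicted directions |
|---|---|---|---|
| 0 | 61% | 55% | 13% |
| 0.3 | 75% | 61% | 9% |
| 0.5 | 87% | 64% | 6% |

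If Bonferroni counts three pairwise comparisons (0.05/3), at least one baseline contrast is significant in 50% to 55% of trials and both in 4% to 9%. Section 13 does not give the count.

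For DTBZ, the pooled paired t-test (n = 30, 0.778 SD in controls only, 400,000 simulated trials) is significant in 48%.

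**4. The same rules by group, in 15 non-responding patients.** For raclopride, at least one contrast is significant in 3% to 4% of trials and both in under 0.1%. For DTBZ the figure is 5%, the nominal level.

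**5. What a group difference in change could deliver.** Two-sample comparison of individual changes, in SD units of the change:
- 95% CI half-width at 15 per group: t(28, 0.975) × √(2/15) = 2.048 × 0.365 = 0.75 SD.
- At 10 per group (15 is a maximum): t(18, 0.975) × √(2/10) = 2.101 × 0.447 = 0.94 SD.
- Difference detectable with 80% power at 15 per group: 1.06 SD, which is 1.06/0.778 = 1.36 times the benchmark.
- Power at 15 per group if a 0.778 SD effect is present in one group only: 54%.

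**The case against.** **The documents point to analysis by group.** Section 2 describes patients and a comparison control group. Section 3 covers both groups and predicts the change in each. Section 5.1 powers a sample of 15 with each group capped at 15, whereas pooling would make it 30. No text supports pooling. This stands: the pooled figures show what would follow if the wording were applied that way, and do not describe what the sponsor intends. What remains is that Section 13 does not state the rule, and analysis by group would still not estimate the group difference.

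**Disease dependence is not a formal hypothesis.** It is a reason given in the background, absent from the hypotheses, endpoints and power statement. This also stands. It argues for a supportive estimate rather than a powered test, but not for having no analysis of the stated reason for up to 15 extra subjects.

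**Stronger readings that the documents do not support.**
- A reader might infer that the primary test will mix patients and controls. Nothing says so.
- A reader might infer that the sponsor will compare the two groups' p-values. No such comparison is planned.
- A reader might convert the SD-unit results into percentage-point limits using the pilot changes. Section 5.1 gives no SD and does not say whether its power refers to the overall time test or to a contrast, so no upper limit follows.
- A reader might treat an added interaction test as settling disease dependence. The groups are not randomised, Section 9 allows stable antidepressants for cataplexy, and the estimate is imprecise.

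**Conclusion.** The concern holds in this form: no planned analysis estimates the group difference in change, and Section 13 does not state that its tests are run by group. The first part rests on the text alone and needs no assumed figure.

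The second is an ambiguity with a likely intended answer. Its possible cost is about 55% to 64% against 3% to 4% for at least one raclopride contrast, and about 48% against 5% for DTBZ. The full biphasic pattern would appear less often, in about 6% to 13% of pooled trials. These figures assume a response in controls only, 0.78 SD, 15 per group, equal SDs and two-sided 0.05, with Bonferroni for two contrasts in the raclopride figures.

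This should be fixed before analysis. It does not invalidate the within-group tests, which can be carried out once the rule is written down.

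**What to change.** **Section 13, raclopride.** Fit group, time and group-by-time with unstructured covariance. Test time within each group and keep the existing Bonferroni step within each group, stating how many comparisons it counts. Read patients on their own for the aim at the end of Section 2, and both groups for the Section 3 prediction. Report the between-group difference in change at 1 h and at 7 h with 95% CIs.

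**Section 13, DTBZ.** Report the paired change within each group, and the group difference in change with a 95% CI.

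**Labelling.** Call the group differences supportive estimates from non-randomised groups, note the antidepressants allowed in Section 9, and do not present them as the answer to the disease-state question. State that a non-significant interaction is not evidence of equal effects.

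**Section 5.1.** State that the power above 80% covers within-subject contrasts in one group of 15 only.

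**Cost.** Wording in two sections and a little more analysis, with no extra subjects or scans. The downside is the imprecision shown in the working, which should be stated beside the estimate.

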## **14. DATA MANAGEMENT AND RETENTION**

A Case Report Form (CRF) will be completed for each subject enrolled in the study. Investigators will protect privacy by assigning an identification code to each (i.e. Jazz-001). A master list containing ID codes matched to the subject's complete name and contact information will be held in a secure file, separate from the CRF. A subject screening log, noting reasons for screen failure, where applicable, will be maintained for all.

Digital files of PET and MRI data will be considered source documents and will be stored on a password-locked computer. The CRF will note the day and time of the PET scan, its number in the PET Centre Database, the radiotracer information (injected radioactivity, specific activity, total mass, etc.) and a note to the effect that the scan was completed with no technical problems.

Study data and other essential documents will be retained in a secure setting by the investigators for a period of 25 years as required by federal regulations.

## **15. REGULATORY ISSUES**

### **15.1. Ethics Approval**

Prior to initiation, this study will have received approval from CAMH REB as well as Health Canada No Objection Letter (NOL). CAMH REB approval is subject to annual renewal. Any amendments to the study will require approval from the above agencies prior to implementation, except when necessary to eliminate immediate hazards and/or protect the safety, rights or welfare of subjects.

### **15.2. Consent**

Consent to enter the study must be sought from each subject only after a full explanation has been given, an information sheet offered and time allowed for consideration. Signed informed consent will be obtained prior to conducting any study procedures (with the exception of the initial phone screen). The right of the subject to refuse to participate without giving reasons must be respected. All subjects are free to withdraw at any time from the protocol treatment without giving reasons and without prejudicing further treatment.

